#### **8.2.1. TEAEs**

The proportion of subjects who have a TEAE during each DB treatment period will be summarized by treatment group for the FAS1 and FAS2.

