### 4.2. SECONDARY ENDPOINTS

Secondary endpoints for each DB period are:

- The proportion of subjects with treatment-emergent adverse events (TEAEs) after study drug compared between DFN-15 and placebo.
- The proportion of subjects who are free from nausea, photophobia, and phonophobia at 15, 30, and 45 minutes and 1, 1.5, 2, 4, and 24 hours postdose compared between DFN-15 and placebo.
- Time to meaningful pain relief (defined as based on subject's perception) within 2 hours postdose compared between DFN-15 and placebo in each treated attack.
- Time to pain freedom within 2 hours postdose compared between DFN-15 and placebo.
- The proportion of subjects who have pain relief at 15, 30, and 45 minutes and 1, 1.5, 2, 4, and 24 hours postdose compared between DFN-15 and placebo. Headache pain relief is defined for DB1 as a reduction from moderate or severe pain prior to dosing to mild or none postdose, and for DB2 as moderate or severe pain predose reduced to mild or none postdose, or mild pain predose reduced to none postdose.
- The proportion of subjects who are pain-free at 15, 30, and 45 minutes and 1, 1.5, 2 (DB2 period), 4, and 24 hours postdose compared between DFN-15 and placebo.
- The proportion of subjects with their Screening MBS (and have this symptom predose) absent at 15, 30, and 45 minutes, and 1, 1.5, 2 (DB2 period), 4, and 24 hours postdose compared between DFN-15 and placebo.
- Change in functional disability score at 2, 4, and 24 hours postdose compared between DFN-15 and placebo.
- Among those reporting cutaneous allodynia predose, the proportion of subjects who are pain-free at 2 and 4 hours postdose compared between DFN-15 and placebo.

- The proportion of subjects who are pain-free at 2 and 4 hours postdose whose BMI is < 30 vs. subjects whose BMI is  $\geq$  30, and whose BMI is < 25 vs. subjects whose BMI is  $\geq$  25.
- The proportion of subjects who have pain recurrence between 2 to 24 hours (i.e., pain-free at 2 hours postdose, with pain [mild, moderate, or severe] reported at 24 hours postdose) compared between DFN-15 and placebo.
- The proportion of subjects who have sustained pain relief at 2 to 24 hours postdose (i.e., pain relief at 2 hours postdose, with no use of rescue medication and no worsening of headache pain within 2 to 24 hours postdose) compared between DFN-15 and placebo.

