### 5.3. SAFETY SET

The Safety Set (SS) will include all subjects who took at least one dose of DB study drug during one or both treatment periods, and have it recorded in their eDiary. Subjects will be analyzed according to the treatment they receive. The Safety Set 1 (SS1) will include randomized subjects who took at least one dose of DB study drug during the DB1 treatment period. The Safety Set 2 (SS2) will include subjects who were re-randomized and took at least one dose of DB study drug during the DB2 treatment period. The SS, SS1, and SS2 will be used for all analyses of safety endpoints including summaries of TEAEs, ECGs, and clinical laboratory results.

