### 5.4. FULL ANALYSIS SET

Each DB treatment period will have a Full Analysis Set (FAS). The Full Analysis Set 1 (FAS1) will include all randomized subjects who took at least one dose of study drug during the DB1 treatment period and have at least one post-baseline efficacy time point assessment for either pain or symptom (among nausea, photophobia, phonophobia) in DB1. The Full Analysis Set 2 (FAS2) will include all re-randomized subjects who took at least one dose of study drug during the DB2 treatment period and have at least one post-baseline efficacy time point assessment for either pain or symptom (among nausea, photophobia, phonophobia). Subjects in the DB1 will be analyzed according to their randomized treatment. Subjects in the DB2 will be analyzed according to their re-randomized treatment. The FAS1 and FAS2 will be used for all analyses of efficacy endpoints.

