### **8.2. SECONDARY ENDPOINTS AND ANALYSES**

The secondary endpoints that involve proportions of subjects who have a response will be summarized by treatment group and will be analyzed using the LOCF for missing secondary efficacy endpoint data.

Secondary endpoint analyses will be conducted as indicated for the FAS1 and FAS2 and will exclude subjects who took rescue medication prior to the data collection of the 2

hours postdose time point (inclusive; LOCF). For all secondary endpoint analyses in DB1 for the FAS1, subjects who have predose pain level = mild (Grade 1) or none (Grade 0) will also be excluded. For all secondary endpoint analyses in DB2 for the FAS2, subjects who have predose pain level = none (Grade 0) will also be excluded.

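### SAP 8.2.1 reports the TEAE secondary endpoint on FAS1/FAS2, and SAP 8.2 does not exempt it from the early-rescue and predose-pain exclusions, so dosed subjects drop out of a safety proportion

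*SAP*

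**What the plan says.** SAP 4.2 names the endpoint as its first secondary endpoint: "The proportion of subjects with treatment-emergent adverse events (TEAEs) after study drug compared between DFN-15 and placebo". Its analysis is in SAP 8.2.1: "The proportion of subjects who have a TEAE during each DB treatment period will be summarized by treatment group for the FAS1 and FAS2".

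The general rules for that part of the SAP are in 8.2:

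- Rescue: "Secondary endpoint analyses will be conducted as indicated for the FAS1 and FAS2 and will exclude subjects who took rescue medication prior to" the 2-hour data collection, with that time point included.
- DB1 predose pain: "For all secondary endpoint analyses in DB1 for the FAS1, subjects who have predose pain level = mild (Grade 1) or none (Grade 0") are removed as well.
- DB2 predose pain: "For all secondary endpoint analyses in DB2 for the FAS2, subjects who have predose pain level = none (Grade 0) will also be excluded".

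SAP 5.4 defines the sets that 8.2.1 uses. Besides a dose, a subject must "have at least one post-baseline efficacy time point assessment for either pain or symptom". On grouping it says: "Subjects in the DB1 will be analyzed according to their randomized treatment". The same rule applies in DB2 with the re-randomized treatment.

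SAP 5.3 gives a different home for these data: "The SS, SS1, and SS2 will be used for all analyses of safety endpoints including summaries of TEAEs, ECGs, and clinical laboratory results". Subjects in those sets are grouped by the treatment they received. SAP 9.3 then plans the adverse event tables, including a row for any TEAE, on SS, SS1 and SS2.

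**The concern.** The exclusions in 8.2 were built around pain and symptom response. Early rescue confounds a 2-hour efficacy reading, and a subject with mild or no pain at dosing cannot meet the DB1 response definitions. Neither reason carries over to adverse events. A subject who swallowed the study drug is at risk of a TEAE whatever the predose pain grade and whatever was taken 90 minutes later.

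The rescue rule deserves most attention because it selects on an event after dosing. Rescue may depend on treatment, so the two arms could lose different shares of subjects. The time frames also do not match: SAP 6.2.5 counts TEAEs for up to 5 days after the dose (in DB1, or until the DB2 dose if that comes first), yet a rescue dose in the first 2 hours would remove the subject from 8.2.1 for that whole window.

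At stake is the TEAE proportion in the section written for the secondary endpoint. It could differ from the any-TEAE row in 9.3 for the same period and arm, and the SAP does not say which of the two answers the endpoint in 4.2.

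**Working it through.** The documents give no figure to reproduce for this point, so the check compares the passages and then bounds the possible gap.

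**Which subjects count, as written**

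| | SAP 8.2.1 under 8.2 and 5.4 | SAP 5.3 and 9.3 |
|---|---|---|
| Took study drug in the period | required | required |
| Post-baseline pain or symptom entry | required | not required |
| Rescue by the 2-hour assessment | removed | kept |
| Predose pain mild or none (DB1), none (DB2) | removed | kept |
| Grouping | as randomized (5.4) | as received |

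**Do the exclusions reach TEAEs?** The two predose-pain sentences cover all secondary endpoint analyses in their period. The rescue sentence covers secondary endpoint analyses without qualification. TEAEs are a secondary endpoint in 4.2, and 8.2.1 is the first subsection under 8.2. Neither 8.2 nor 8.2.1 contains an exemption, so the literal answer is yes.

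**Does any other passage support this?** Protocol 10.4.2 lists TEAEs among the endpoints under the efficacy heading, and protocol 10.2 and 10.5.1 put efficacy analyses on the FAS. SAP 9 names FAS1 and FAS2 next to the safety sets for safety analyses. These passages support a FAS display, but none applies the rescue or predose-pain exclusions to adverse events. SAP 11, which lists changes from the protocol, mentions those exclusions only for the co-primary analyses. Protocol 10.5.6 tabulates TEAEs by treatment received.

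**How large can the gap be?** For one arm in one period, let

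- f = share of dosed subjects left out of 8.2.1,
- k = TEAE rate in those kept,
- e = TEAE rate in those left out.

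The rate in all dosed subjects is (1 − f) × k + f × e. Section 8.2.1 reports k. Hence

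gap = k − [(1 − f) × k + f × e] = f × (k − e).

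Since k and e both lie between 0 and 1, |k − e| ≤ 1 and |gap| ≤ f. The gap is zero if those left out have the same TEAE rate as those kept, negative if their rate is higher, and positive if it is lower. For the DFN-15 minus placebo difference, the shift is f₁ × (k₁ − e₁) − f₀ × (k₀ − e₀), where 1 is DFN-15 and 0 is placebo. It cannot exceed f₁ + f₀ in absolute value. This bound leaves aside any difference between randomized and received treatment. The documents give no value for f, k or e, so the calculation stops here.

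**The case against.** The strongest reply is that the SAP plans two displays: a safety-set table under 9.3 and an additional FAS table under 8.2.1. SAP 9 names both kinds of set, and 5.3 does not say that only the safety sets may be used. This stands as far as the choice of set goes. A reader might infer that a FAS display of TEAEs is itself barred, and the documents do not support that. The reply does not explain why the FAS display should also lose early rescuers and subjects dosed at low pain.

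A second reply is that 8.2 was drafted with efficacy in mind: its opening sentence deals with missing efficacy data, and its rescue rule is tied to the 2-hour time point and to LOCF. That is plausible. It also counts against a reader who infers a deliberate decision to filter safety data, since nothing shows such intent. But the exclusion sentences carry no efficacy limit, and a programmer would have to guess.

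A third reply concerns grouping. SAP 5.4 points to randomized treatment for the FAS, whereas SAP 6.1.1 defines treatment group as the regimen applied in the period, and 8.2.1 summarizes by treatment group. So it is not established that 8.2.1 groups subjects as randomized; the text is ambiguous.

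Finally, early rescue and DB1 dosing at mild or no pain both depart from instructions (protocol 8.5.2 and 5.1), so the excluded share may be small. This stands, although the documents do not quantify it.

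**Conclusion.** Wrong as written, with a limited consequence; worth correcting before the analysis is run (severity: consider). The literal text removes dosed subjects from a safety proportion, in part because of a post-dose event, and 8.2.1 and 5.3 name different sets for TEAE summaries without saying how the two displays relate.

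Three stronger conclusions might be inferred, and the documents support none of them:

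- **That adverse events go unreported.** SAP 9.3 plans TEAE tables on SS, SS1 and SS2, together with listings of all adverse events.
- **That a test or the trial's success is affected.** Section 8.2.1 plans no p-value, and success rests on the co-primary endpoints (SAP 8.1.1).
- **That the TEAE rate is understated.** The direction depends on whether those left out have more or fewer TEAEs than those kept, which the documents do not show.

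The size is undetermined. Within an arm the gap cannot exceed the share of dosed subjects left out. This rests on the literal reading of 8.2; if the sponsor meant the exclusions for efficacy only, a clarifying sentence removes that part of the problem.

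**What to change.** 1. In SAP 8.2, state that the rescue and predose-pain exclusions apply to efficacy endpoints only.
2. In SAP 8.2.1, report the TEAE endpoint on SS1 and SS2 by treatment received, and refer to the tables in 9.3.
3. If a FAS display of TEAEs is still wanted, label it supplementary and state how subjects are grouped.
4. Make the opening sentence of SAP 9 consistent with 5.3.

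The cost is wording only. The SS1 and SS2 tables are already planned in SAP 9.3, and no data collection, sample size or test changes.

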#### **8.2.2. Freedom from Nausea, Photophobia, and Phonophobia Postdose**

The proportion of subjects who are free from nausea, photophobia, and phonophobia at 15, 30, and 45 minutes and 1, 1.5, 2, 4, and 24 hours postdose during each DB treatment period will be summarized by symptom, treatment group, and time point for the FAS1 and FAS2. The corresponding p-values from Fisher's exact test will be computed for the comparison between treatment groups. Subjects who report a symptom predose and report the status of the symptom at the particular postdose time point will be analyzed.

#### **8.2.3. Time to Pain Relief and Pain Freedom Postdose**

The following two secondary efficacy endpoints are captured in the subject eDiary separately from the scheduled time points, and are self-initiated based on the actual time of a subject's perception of pain relief and pain freedom (if they occur) within the first 2 hours postdose. Descriptive statistics for the two endpoints will be provided by treatment group for the FAS1 and FAS2. Additionally, the two endpoints will be summarized and graphically presented by treatment group for the FAS1 and FAS2 using Kaplan-Meier survival estimation. Comparisons between treatment groups will be performed using the log-rank test.

##### **8.2.3.1. Time to Meaningful Headache Pain Relief Postdose**

Time to meaningful headache pain relief is defined as the time in minutes from the time a subject takes study drug until the time a subject indicates meaningful pain relief in the eDiary within 2 hours postdose. The time to meaningful headache pain relief postdose will be summarized and analyzed using Kaplan-Meier survival estimation for the FAS1 and FAS2. The corresponding p-values from a log-rank test will be computed for the comparison between treatment groups.

##### **8.2.3.2. Time to Headache Pain Freedom Postdose**

Time to headache pain freedom is defined as the time in minutes from the time a subject takes study drug until the time a subject indicates pain freedom in the eDiary within 2 hours postdose. The time to headache pain freedom postdose will be summarized and analyzed using Kaplan-Meier survival estimation for the FAS1 and FAS2.

The corresponding p-values from a log-rank test will be computed for the comparison between treatment groups.

#### **8.2.4. Headache Pain Relief Postdose**

The proportion of subjects who have pain relief at 15, 30, and 45 minutes and 1, 1.5, 2, 4, and 24 hours postdose will be summarized by treatment group and time point for the FAS1 and FAS2. For DB1, headache pain relief is defined as a reduction in migraine pain from predose severe or moderate to mild or none postdose. For DB2, headache pain relief is defined as moderate or severe pain predose reduced to mild or none postdose, or mild pain predose reduced to none postdose. The corresponding p-values from Fisher's exact test will be computed for the comparison between treatment groups. Subjects who report a headache predose and rate the headache pain level at the particular postdose time point will be analyzed.

#### **8.2.5. Headache Pain Freedom Postdose**

The proportion of subjects who are pain-free at 15, 30, and 45 minutes and 1, 1.5, 2 (DB2 period), 4, and 24 hours postdose during each DB treatment period will be summarized by treatment group for the FAS1 and FAS2. The corresponding p-values from Fisher's exact test will be computed for the comparison between treatment groups.

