**Treatment:**

For the DB1 period, all subjects will be randomly assigned in a 1:1 ratio to receive either DFN-15 or a matching placebo to be used to treat 1 migraine attack as soon as (and no more than within 1 hour after) experiencing moderate to severe pain. Eligible subjects will then be re-randomized in a 1:1 ratio into the DB2 period to receive either DFN-15 or a matching placebo to treat another migraine attack at any pain level. The migraine attacks and associated treatment and assessments are to be recorded in an eDiary.

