#### **10.7 Determination of Sample Size**

Approximately 600 subjects will be randomized for the DB1 period. Subjects who discontinue participation without completing the study protocol will not be replaced.

The first co-primary endpoint is the comparison of the proportion of subjects who are pain-free at 2 hours after the first dose of study drug. It is assumed that 17.6% of placebo and 29.2% of DFN-15 (treated) subjects will be pain-free at 2 hours. A sample size of 600 subjects will provide 88% power to detect this assumed difference between placebo and DFN-15 at a 5% (2-sided) level of significance and with a 15% dropout rate.

The second co-primary endpoint is the comparison of the proportion of subjects who are free from their Screening MBS among nausea, photophobia, and phonophobia at 2 hours after the first dose of study drug. It is assumed that 28.2% of placebo and 44.7% of DFN-15 (treated) subjects will be free from their Screening MBS at 2 hours. A sample size of 480 subjects will provide 94% power to detect this assumed difference between placebo and DFN-15 at a 5% (2-sided) level of significance and with a 15% dropout rate.

Since the sample size for the first co-primary endpoint is larger than that of the second co-primary endpoint, the larger sample size will be used for the study.

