### 5.2. RANDOMIZED SET

Each DB treatment period will have a Randomized Set. The randomized set for DB1 will include all subjects who give informed consent and are eligible for and randomized into the DB1 treatment period. The randomized set for DB2 will include all subjects in the randomized set for DB1 who are eligible for and are re-randomized into the DB2 treatment period.

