## 6. GENERAL ASPECTS FOR STATISTICAL ANALYSIS

### 6.1. GENERAL METHODS

#### 6.1.1. Summary Statistics

In general, descriptive statistical methods will be used to summarize the data from this study. With appropriate sample sizes, hypothesis testing can be performed for the co-primary and secondary efficacy endpoints.

The term “treatment group” refers to the applied treatment regimen during DB1 or DB2 (DFN-15 120 mg or placebo). All data collected during the study will be included in subject data listings. All subjects entered into the database will be included in subject data listings. Unless otherwise noted, the data will be sorted first by treatment group, subject number, and then by date within each subject number.

Unless stated otherwise, the term “descriptive statistics” refers to number of subjects (n), mean, median, standard deviation, minimum, and maximum for continuous data and frequencies and percentages for categorical data.

All categorical/qualitative data will be presented using absolute frequency counts and percentages. The total number of subjects in the treatment group overall (N) in the specified population will be used as the denominator for percentage calculations, unless stated otherwise in the table shell. All percentages will be presented in parentheses with 1 decimal point, unless otherwise specified. Percentages equal to 100 will be presented as 100% and percentages will not be presented for zero frequencies.

Unless specified otherwise, all statistical testing and confidence intervals (CIs) will be 2-sided and will be performed using a significance (alpha) level of 0.05.

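### The DB2 responder endpoints are compared with an unadjusted Fisher's exact test that makes no use of each subject's DB1 treatment and result, so power and precision may be lost in DB2

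*SAP*

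**What the plan says.** The DB2 subjects are DB1 subjects. SAP 5.2 defines the DB2 randomized set as "all subjects in the randomized set for DB1 who are eligible for and are re-randomized into the DB2 treatment period". The Protocol synopsis (Treatment) states: "Eligible subjects will then be re-randomized in a 1:1 ratio into the DB2 period". Under Protocol 9.2.1.3 this happens at Visit 3, within 2 to 7 days of the treated DB1 attack, and the eDiary entries are reviewed at the same visit. The eDiary schedule (Protocol Table 9-2, SAP Table 2) collects the same items in both periods.

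For analysis, SAP 5.4 says: "Subjects in the DB2 will be analyzed according to their re-randomized treatment". SAP 8.2.5 then specifies, for pain freedom in each period: "The corresponding p-values from Fisher's exact test will be computed for the comparison between treatment groups". The same unadjusted test is planned for the other tested FAS2 proportions in SAP 8.2.2, 8.2.4 and 8.2.6 to 8.2.14, and for the exploratory comparisons in 8.3. Testing "will be 2-sided and will be performed using a significance (alpha) level of 0.05" (SAP 6.1.1). The only regression model in the SAP is the FAS1 subgroup model in 8.4. No analysis uses the DB1 result as a covariate for DB2.

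**The concern.** DB1 treatment and DB1 result are fixed before the DB2 randomization, so adjusting for them cannot introduce post-randomization bias, and the data are already collected. If a subject's response in one attack predicts the response in the next, the unadjusted comparison leaves that predictable variation in the error.

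DB2 has a purpose of its own. Protocol 5.2 uses it to see whether efficacy extends across the range of pain levels, and Protocol 10 plans hypothesis tests for all secondary efficacy endpoints. Pain freedom and Screening MBS absence at 2 hours are secondary endpoints specifically for DB2. No DB2 sample size or power is stated, and the DB2 set cannot be larger than the DB1 set. What is at stake is a real DB2 effect being missed more often than the data require.

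**Working it through.** **Inputs from the documents.** Protocol 10.7: "It is assumed that 17.6% of placebo and 29.2% of DFN-15 (treated) subjects will be pain-free at 2 hours" and "A sample size of 600 subjects will provide 88% power to detect this assumed difference between placebo and DFN-15", with 15% dropout. Two-sided alpha is 0.05.

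**Assumptions not in the documents.** The same rates apply in DB2; FAS2 has 400 subjects (checked from 360 to 510); phi between a subject's two attacks is 0 to 0.5.

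**1. The plan's own figure.** Evaluable per arm: 600 × 0.85 / 2 = 255. Power = Φ(z), with z = [d√n − 1.96√(2p̄(1−p̄))] / √(p₀(1−p₀) + p₁(1−p₁)).

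- d = 0.292 − 0.176 = 0.116, and p̄ = 0.234.
- √(2 × 0.234 × 0.766) = 0.5987.
- √(0.1450 + 0.2067) = 0.5931.
- z = (0.116 × 15.97 − 1.96 × 0.5987) / 0.5931 = 1.145, so power is 87.4%. The stated 88% reproduces.
- Fisher's exact test on the same numbers, by full enumeration, has 85.5%.

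**2. The planned DB2 test at 200 per arm.** Chi-square: z = (0.116 × 14.14 − 1.1735) / 0.5931 = 0.787, power 78.5%. Exact Fisher: 75.2%. The difference of about 3 points is Fisher's conservatism and has nothing to do with DB1. At 180, 217 and 255 per arm, Fisher's test has 70.3%, 78.9% and 85.5%.

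**3. Adding the DB1 information.** Trials were simulated with correlated binary DB1 and DB2 outcomes (latent normal) and independent 1:1 randomization in each period. The CMH statistic over strata k is

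z = Σ(A − m₁Y/M) / √Σ[m₁(M−m₁)Y(M−Y) / (M²(M−1))]

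where, in DB2, A is the number of DFN-15 responders, m₁ the number on DFN-15, Y all responders and M the stratum size. Power at N = 400:

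| phi | Fisher | chi-square | CMH, 4 strata (DB1 arm × response) | CMH, 6 strata, 15% DB1 results missing |
|---|---|---|---|---|
| 0 | 74-76% | 78-80% | 78% | 78% |
| 0.1 | 74-76% | 78-80% | 79% | 79% |
| 0.2 | 74-76% | 78-80% | 81% | 80% |
| 0.3 | 74-76% | 78-80% | 81% | 80% |
| 0.5 | 74-76% | 78-80% | 88% | 87% |

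Separate runs at N = 400 gave 79.3% at phi 0.2, 82.4% at 0.3 and 88.6% at 0.5 (4 strata), which indicates the Monte Carlo spread.

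**4. Hand check.** At N = 434 the simulated ratio of adjusted to unadjusted variance of the risk difference is 0.98, 0.93 and 0.77 at phi 0.2, 0.3 and 0.5. Dividing 200 per arm by these gives effective sizes of 204, 215 and 260. The formula in step 1 then gives z = 0.815, 0.890 and 1.173, or 79%, 81% and 88%. This agrees with the table.

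**5. Other sizes, phi 0.3.** N = 360: Fisher 70%, CMH 78%. N = 434: 78%, 84%. N = 510: 86%, 91%.

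**6. Error rate with no DB2 effect.** CMH 4.9-5.3%; Fisher 3.4-4.6%.

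**7. Splitting the gain.** Against the chi-square test, DB1 adds about 0 points at phi 0-0.1, 1 at 0.2, 2-3 at 0.3 and 8-9 at 0.5. The remaining 3-4 points over Fisher's test are its conservatism.

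**The case against.** The strongest reply is that nothing is broken. Fisher's test is a valid, slightly conservative two-sample comparison; re-randomization makes it unbiased, and its error rate already allows for chance imbalance in DB1 history. It is also the test used throughout the plan, including for the co-primaries. All of that stands: this is a question of efficiency between two valid analyses.

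The second reply is that the loss is conjectural. The documents give no correlation, and DB1 attacks are moderate or severe while DB2 attacks are at any pain level, so DB1 may predict DB2 poorly. This also stands. At phi of 0.1 or less the DB1 information adds nothing, and nothing in the documents supports a value as high as 0.5. Missing DB1 results dilute the gain: with 30% assumed missing at phi 0.3, CMH has 80.8% against 79.0% for chi-square.

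The third reply concerns sparse endpoints. Recurrence, the allodynia subset and the earliest time points may have too few events for stratification, and a loosely worded fallback would let the data choose the test. That is a fair constraint on the fix.

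A reader might also infer that the two periods should be pooled. In the simulations a pooled model has 96% power or more, but it tests a common effect. With a real DB1 effect and no DB2 effect it rejects in 55-69% of trials, so it does not answer the DB2 question.

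**Conclusion.** The point holds as a possible loss of efficiency in secondary DB2 comparisons. The planned test ignores legitimate pre-randomization information. Under the stated assumptions the stratified test does not fall below Fisher's at any correlation examined, and it keeps its error rate near 5%. The total gain at 400 subjects runs from about 3-4 points with no correlation to about 12-14 points at phi 0.5 (87-89% against 75%). The part due to DB1 becomes material only from phi of about 0.3.

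Two stronger readings are not supported. A reader might infer that the DB2 test is biased or has a wrong error rate because the same people appear twice. It does not: each DB2 comparison uses one observation per subject and a fresh randomization. A reader might also infer that a known amount of power is lost, or that a planned interval is too wide. The documents give no correlation, DB2 size or DB2 rates, and SAP 8.2.5 and 8.2.6 plan no between-arm interval. Trial success rests on the two DB1 co-primaries (SAP 8.1.1), which this does not touch.

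**What to change.** Before unblinding, amend SAP 8.2 as follows.

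- For 2-hour pain freedom (8.2.5) and 2-hour Screening MBS absence (8.2.6) in FAS2, and for other FAS2 responder endpoints with enough events, make the main test a CMH test stratified by DB1 treatment and by DB1 result on the same endpoint (response, no response, missing or not applicable).
- Report a stratified risk difference with its 95% CI.
- Keep Fisher's test as a supportive result.
- List by name the sparse endpoints and time points where Fisher's test stays the main test, for example recurrence, the allodynia subset and the earliest time points, so that the choice does not depend on the data.

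The cost is SAP text and one derived stratification variable from data already collected. The drawbacks are an asymptotic rather than exact p-value and a different test in DB2 from the one used in DB1.
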